### **Amendment 4** (Issued date: 18 April 2019)

**The overall reason for the amendment:** This protocol amendment is made to reduce the overall number of RSV-seropositive toddlers in the study from 48 to 36. The rationale for this reduction is as follows:

As of 18 April 2019, 35 seropositive toddlers have been enrolled in the current study (VAC18194RSV2001). The IDMC have reviewed available safety and immunogenicity data from the planned interim analysis, unblinded at the group level, when at least 24 toddlers had reached Day 29 or discontinued earlier. As enrollment was staggered over time, the analysis contained solicited and unsolicited AE data post-Dose 1 from 32 toddlers, of whom 30 toddlers already had post-Dose 2 data and 28 were in follow-up.

The IDMC concluded that the safety profile was acceptable and supported progression to the next study (VAC18194RSV2002) in RSV-seronegative toddlers aged 12 to 24 months in which subjects will receive half the dose of Ad26.RSV.preF used in the current study (ie,  $2.5 \times 10^{10}$  vp). In addition, blinded safety review by the sponsor of additional data since the IDMC review has not revealed any safety concerns. Study VAC18194RSV2002 has already been initiated; as of 18 April 2019, 6 seronegative toddlers have been enrolled and have received their first vaccination.

The reduction in the number of seropositive toddlers in the current study is supported by the expectation that there would be no difference in the local and systemic reactogenicity between seropositive and seronegative toddlers. The collection of safety data at the planned dose in seronegative toddlers in study VAC18194RSV2002 will therefore add to the overall safety database in this age group as planned. Furthermore, as RSV-seropositive toddlers are at limited to no risk of severe RSV disease, there would be limited value in continuation of the study.

*The table below gives an overview of the rationale for each change and all affected sections*

**Rationale:** As indicated above, the number of RSV-seropositive toddlers in this study is reduced from 48 to 36.

*Synopsis: Overview of Study Design; Sample Size Determination*

*3.1 Overview of Study Design*

*11.2 Sample Size Determination*

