### Exploratory Endpoints – RSV Infection

- For Cohort 1 only, RSV infection confirmed by either reverse transcriptase polymerase chain reaction (RT-PCR), or by serology for, but not limited to, protein G and/or N if no RT-PCR is available. To detect asymptomatic RSV infections, a fold increase will be applied to call a subject seropositive to G and/or N ELISA (or F in case of placebo subjects). Fold increases for RSV infection will be determined based on the (suspected) infection and the convalescent blood samples.
- In Cohort 1 throughout the study:
  - Severe RSV-LRTI
  - RSV medically-attended respiratory tract infection (MA-RTI)

Refer to Section 9.2 for evaluations related to endpoints.

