Outside of the RSV season, nasal turbinate samples will only be collected from subjects with MA-RTIs or severe LRTIs (for definition of MA-RTI and severe LRTI, please refer to Section 11.3.1).

Throughout the study, nasal turbinate samples will be collected from any subject with a MA-RTI or severe LRTI.

The criteria used to assess potential cases of RSV infection in subjects from Cohort 1 will be as follows:

- Suspected RSV infection: subject has persistent (>48 hours) clinical symptoms of rhinitis (sneezing or runny nose or congestion) and persistence (>24 hours) of one or more of the following: cough, abnormal breathing, fever, lethargy or decreased appetite.

Occurrence of this combination of symptoms in any subject would trigger collection of a nasal turbinate sample.

---

a These procedures should preferentially be performed at the study site. These procedures can be conducted at the subject's home by site staff or qualified professional staff if the study site has an established standard operating procedure as such. In case of emergency, the procedures can be done in a hospital.

- Confirmed RSV infection: subject with suspected RSV infection and positive for RSV on the basis of RT-PCR conducted centrally.

Data on the clinical course of infection including information regarding oxygenation status, supplemental oxygen requirements and specific drug treatments should be collected, as well as any other concurrent respiratory illness present at the time of the diagnosis of the event and up to symptom resolution.

To ensure the rapid follow-up of any severe LRTI or MA-RTI, study sites will need to make arrangements with primary care physicians, emergency departments and/or hospitals' urgent care facilities to be notified when a subject is being seen. Further details will be provided in the Trial Center File. Any parent/legal guardian who seeks medical attention for their child due to an RTI should make the attending health care professional aware that their child is taking part in an RSV vaccine study. Each child's parent/legal guardian will be given a wallet card with key study information and site contact details (see Section 12.3.1). These details should be shared with the attending health care professional.

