#### **11.6. RSV Infection**

Incidence of any RSV infection, as described in Section 3.2, in Ad26.RSV.preF and placebo subjects will be summarized by descriptive statistics.

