### *Exploratory Objectives*

- To further assess the humoral and cellular immune responses elicited by Ad26.RSV.preF. The assays to be used may include, but are not limited to, RSV strain cross-neutralization, anti-F protein antibody specificity and functionality characterization, adenovirus neutralization assays, molecular antibody characterization (avidity, Fc cell interaction, antibody isotyping), evaluation of the cellular immune response (interferon gamma [IFN $\gamma$ ] enzyme-linked immunospot [ELISpot] assay) and functional and memory immune response (by ICS), and cytokine profiles of RSV F-protein peptide-stimulated peripheral blood mononuclear cell (PBMC) supernatant.
- To assess RSV infection rates in Ad26.RSV.preF and placebo subjects.
- To monitor for severe RSV-lower respiratory tract infection (LRTI) in Cohort 1 (RSV-seropositive toddlers aged 12 to 24 months).
- To assess symptoms of respiratory illness via the respiratory tract infection (RTI) symptoms

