## **1.6. Changes to planned analyses**

Two addition interim analyses for Cohort 1 have been added, for the purpose of informing future vaccine-related decisions in a timely manner. The first interim analysis will be performed when 12 subjects have reached Day 8, and the second one when at least 12 subjects have reached Day 29. Given that the first interim analysis coincides with the planned IDMC analysis, the IDMC members will receive immediately unblinded at the group level safety results instead of blinded, as specified in the CTP. That way the IDMC and the study team will possess the same information regarding safety. Moreover, the conduct of the planned interim analysis, when at least 24 subjects of Cohort 1 have reached Day 29 (28 days post-Dose 1) or discontinued earlier, will be dependent on the outcome of the previous interim analyses and is at the discretion of the sponsor.

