## 3. DATA MONITORING COMMITTEE REVIEW

An independent data monitoring committee (IDMC) will be established to monitor severe LRTI. The presence of severe LRTI will be determined by the Clinical Endpoint Committee (CEC), a separate committee (see CTP Section 11.9.2). The outcome of the adjudication of the CEC as well as the determination of RSV positivity will be provided to the IDMC.

The IDMC will review 7-day post-dose 1 safety data of the first 12 Cohort 1 subjects and will convene as needed on an ad hoc basis to ensure the continuing safety of the subjects enrolled in this study. The IDMC will also convene to discuss any situation that meets a study vaccination pausing rule. The IDMC will monitor severe RSV-LRTI as detailed in the IDMC charter. A separate SAP for the IDMC analysis will be provided.

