## 7. RSV INFECTIONS

In case of a severe LRTI being present in Cohort 1, then all potential cases of RSV infection will be summarized in the following two categories and based on their severity (severe/ non-severe).

- Suspected RSV infection: subject has persistent (>48 hours) clinical symptoms of rhinitis (sneezing or runny nose or congestion) and persistence (>24 hours) of one or more of the following: cough, abnormal breathing, fever, lethargy or decreased appetite. Occurrence of this combination of symptoms in any subject would trigger collection of a nasal turbinate sample.
- Confirmed RSV infection: subject with suspected RSV infection and positive for RSV on the basis of RT-PCR conducted centrally.

**ATTACHMENTS****Attachment 1: Guidance for Industry: Toxicity Grading Scale for Healthy Adult and Adolescent Volunteers Enrolled in Preventive Vaccine Clinical Trials**

The laboratory values provided in the tables below serve as guidelines and are dependent upon institutional normal parameters. Institutional normal reference ranges should be provided to demonstrate that they are appropriate.

If a laboratory value falls within the grading as specified below but also within the local laboratory normal limits, the value is considered as normal.

Serum *	Mild (Grade 1)	Moderate (Grade 2)	Severe (Grade 3)	Potentially Life Threatening (Grade 4)**
Sodium – Hyponatremia mEq/L	132 – 134	130 – 131	125 – 129	< 125
Sodium – Hypernatremia mEq/L	144 – 145	146 – 147	148 – 150	> 150
Potassium – Hyperkalemia mEq/L	5.1 – 5.2	5.3 – 5.4	5.5 – 5.6	> 5.6
Potassium – Hypokalemia mEq/L	3.5 – 3.6	3.3 – 3.4	3.1 – 3.2	< 3.1
Glucose – Hypoglycemia mg/dL	65 – 69	55 – 64	45 – 54	< 45
Glucose – Hyperglycemia Fasting – mg/dL Random – mg/dL	100 – 110 110 – 125	111 – 125 126 – 200	>125 >200	Insulin requirements or hyperosmolar coma
Blood Urea Nitrogen BUN mg/dL	23-26	27 – 31	> 31	Requires dialysis
Creatinine – mg/dL	1.5 – 1.7	1.8 – 2.0	2.1 – 2.5	> 2.5 or requires dialysis
Calcium – hypocalcemia mg/dL	8.0 – 8.4	7.5 – 7.9	7.0 – 7.4	< 7.0
Calcium – hypercalcemia mg/dL	10.5 – 11.0	11.1 – 11.5	11.6 – 12.0	> 12.0
Magnesium – hypomagnesemia mg/dL	1.3 – 1.5	1.1 – 1.2	0.9 – 1.0	< 0.9
Phosphorous – hypophosphatemia mg/dL	2.3 – 2.5	2.0 – 2.2	1.6 – 1.9	< 1.6
CPK – mg/dL	1.25 – 1.5 x ULN***	1.6 – 3.0 x ULN	3.1 – 10 x ULN	> 10 x ULN
Albumin – Hypoalbuminemia g/dL	2.8 – 3.1	2.5 – 2.7	< 2.5	--
Total Protein – Hypoproteinemia g/dL	5.5 – 6.0	5.0 – 5.4	< 5.0	--

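### SAP 7 makes the RSV-infection summary depend on a severe LRTI in Cohort 1 and names no vaccine group, although protocol 11.6 promises it by group without condition

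*SAP*

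**What the plan says.** Protocol 11.6 states: "Incidence of any RSV infection, as described in Section 3.2, in Ad26.RSV.preF and placebo subjects will be summarized by descriptive statistics". No condition is attached, and both groups are named. This serves an exploratory objective in protocol 2.1.1, which SAP 1.1 repeats: "To assess RSV infection rates in Ad26.RSV.preF and placebo subjects".

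SAP 7 is the only place in the SAP that specifies a summary of RSV infection. It opens: "In case of a severe LRTI being present in Cohort 1, then all potential cases of RSV infection will be summarized". It then gives two categories, suspected and confirmed, split into severe and non-severe. It mentions neither vaccine group nor regimen.

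SAP 1.6, which lists departures from the protocol, begins: "Two addition interim analyses for Cohort 1 have been added, for the purpose of informing future vaccine-related decisions in a timely manner". The rest of that section covers what the IDMC receives and the now optional interim analysis at 24 subjects. The RSV-infection summary does not appear.

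Three other passages bear on the point:

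- **Trigger.** SAP 3 says: "The presence of severe LRTI will be determined by the Clinical Endpoint Committee (CEC), a separate committee". It treats RSV positivity as a separate determination.
- **Expected risk.** The Amendment 4 rationale reduces the sample size partly "as RSV-seropositive toddlers are at limited to no risk of severe RSV disease".
- **Definition.** Protocol 3.2, copied in SAP 7, has: "Confirmed RSV infection: subject with suspected RSV infection and positive for RSV on the basis of RT-PCR conducted centrally". Protocol 2.1.2 has: "For Cohort 1 only, RSV infection confirmed by either reverse transcriptase polymerase chain reaction (RT-PCR), or by serology".

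**The concern.** The protocol promises an output, and the SAP makes that output depend on an event that may not occur. If no severe LRTI is adjudicated, nothing in the SAP requires a count of RSV infections in either group, however many RT-PCR positives there are.

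The adverse event tables do not fill the gap. Under protocol 9.2.3.1, RTIs go on the AE page only when they fall within 28 days of a dose, unless they are serious or a severe LRTI. A non-serious RTI in the RSV season but outside those windows is sampled, tested by RT-PCR and recorded on the RTI Symptoms Form. If it is positive, no SAP-specified table shows it unless a severe LRTI has also occurred. The protocol schedules 14-day in-season calls and nasal sampling to find such cases.

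A linked question is whether the confirmed category in SAP 7 would capture every RT-PCR positive.

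**Working it through.** **1. The texts side by side.**

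| Item | Protocol 11.6 | SAP 7 |
|---|---|---|
| Condition | None | A severe LRTI in Cohort 1 |
| Vaccine groups | Active and placebo named | None named |
| Breakdown | Infection as in section 3.2 | Suspected/confirmed, severe/non-severe |
| Declared as a change | n/a | Not in SAP 1.6 |

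**2. What the trigger means.** SAP 3 separates severe LRTI from RSV positivity, so the trigger reads as severe LRTI of any cause. If severe RSV-LRTI was meant, the condition is narrower and would be met no more often.

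**3. The plan's own calculation.** The table in protocol 11.2 uses 1 − (1 − p)^N. For N = 24 and p = 0.5%, 1%, 2.5%, 5% and 10% this gives 11.3%, 21.4%, 45.5%, 70.8% and 92.0%, which matches the printed 11%, 21%, 46%, 71% and 92%. That table is not in dispute. The same binomial model is used next.

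**4. Chance that the summary is never triggered.** Input: 36 toddlers, 24 active and 12 placebo (protocol 3.1, Table 5). The documents give no severe-LRTI rate, so p is assumed, and children are treated as independent. P(no severe LRTI) = (1 − p)^36:

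| Assumed p | P(no event in 36) |
|---|---|
| 0.1% | 96.5% |
| 0.5% | 83.5% |
| 1% | 69.6% |
| 2% | 48.3% |
| 2.5% | 40.2% |
| 5% | 15.8% |
| 10% | 2.3% |

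The even-odds point solves (1 − p)^36 = 0.5, so p = 1 − 0.5^(1/36) = 1.9%. Below that risk the summary is more likely than not to go untriggered. Above it, the condition would usually be met.

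**5. What an unconditional table could show.** With zero infections, the two-sided 95% Clopper-Pearson upper limit is 1 − 0.025^(1/n). For n = 24 this is 14%, and for n = 12 it is 26%. The table would be informative but imprecise.

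**6. The confirmed category.** Protocol 3.2 and SAP 7 require the persistent symptom combination as well as a positive RT-PCR. Protocol 2.1.2 and the RSV-positivity rule in 11.3.1.2 do not. Under protocol 3.2, RTIs within 28 days of a dose, and medically attended RTIs at any time, are sampled without that combination, unless a sample was taken less than 7 days before. A positive from such an RTI would fall outside the confirmed category.

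**The case against.** The strongest reply is that SAP 7 does not cancel protocol 11.6. It never says the summary is made only in that case, and it can be read as describing an extra breakdown for when a severe LRTI occurs. SAP 1 leaves the list of tables to separate data presentation specifications, which are not among the documents and might include an unconditional table. This stands to the extent that one cannot say the table would certainly be missing. It does not remove the conflict: no SAP text requires the summary without the trigger, and a table list would not change the wording of section 7.

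On vaccine group, protocol 11.7 and SAP 5 present safety data by regimen, so a split by group may have been taken for granted. SAP 7 sits outside the safety section and does not invoke that layout. This is the lesser part of the point.

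On the trigger, the limited-risk statement in Amendment 4 concerns severe RSV disease, not severe LRTI of other causes, and protocol 11.3.1 uses the severe LRTI label for the RSV-positive endpoint. Both observations are fair. They are why the risk range above runs to 10% and is illustration only. The contradiction does not depend on it.

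On the definition, SAP 7 follows protocol 3.2, which is where 11.6 points, so the inconsistency belongs to the protocol. Protocol 3.4.5 also describes suspected cases in the 28-day windows separately from those found by the defined symptom set, so exclusion of those positives is not certain. It is also true that endpoint 2.1.2 covers serology and asymptomatic infection, which an RT-PCR row does not.

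**Conclusion.** The concern holds. SAP 7 contradicts protocol 11.6 by adding an undeclared condition, and it drops the comparison groups that 11.6 and the SAP's own objective name. No supplied text requires the output when the condition fails. How likely that is depends on an unknown risk: more likely than not below about 1.9% per child, and unlikely at 5% or above.

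The consequence is modest. The objective is exploratory, no hypothesis is tested, and the comparison is 24 versus 12 children. RTIs within 28 days of a dose still enter the unsolicited AE tables, SAEs are tabulated over the whole study, and CEC and IDMC review is unaffected. What is left without a required output is the RT-PCR-classified infection summary by vaccine group. It should be fixed, but it does not threaten the primary safety conclusions.

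**What to change.** In SAP 7, delete the opening conditional clause. Always tabulate suspected and confirmed RSV infection, by severity, as n/N (%) by vaccine group on the Cohort 1 Full Analysis set. Add one row for any sampled RTI with a positive central RT-PCR, so that positives without the symptom combination are visible. A count of RSV medically attended RTIs is optional, because protocol 11.3.1 collects that endpoint for feasibility. If the sponsor wants to keep the condition, it should be declared in SAP 1.6 with a reason.

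Separately, clarify in the protocol how the confirmed label in 3.2 relates to endpoint 2.1.2 and to 11.3.1.2, including whether serological infections count. Protocol 9.2.2 makes serology on scheduled samples optional, so the SAP change need not wait for this.

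The cost is one deleted clause, the words for vaccine group, and one small table with one extra row. All of it uses data already collected. Both documents already need infection status, because samples taken after a natural RSV infection are left out of the per-protocol immunogenicity set. No new assay or visit is required.

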### Safety Follow-up

Parent(s)/legal guardian(s) of subjects in Cohort 1 will be contacted by telephone (or clinic visit) through 1 year after the first dose (including during the active phase and safety follow-up phase: every 30 days  $\pm$  7 days outside the RSV season, but every 14 days  $\pm$  3 days in season). During each 28-day post-vaccination period, calls will remind parents/legal guardians to contact the site in the event their child develops an RTI. During the RSV season, but outside the 28-day post-vaccination period, calls will remind parents/legal guardians to contact the site in the event their child develops a combination of symptoms of respiratory infection (persistent [ $>48$  hours] clinical symptoms of rhinitis [sneezing or runny nose or congestion] and persistence [ $>24$  hours] of one or more of the following: cough, abnormal breathing, fever, lethargy or decreased

appetite). These calls will also check for any SAEs and associated concomitant medications since the previous visit or telephone contact.

### 3.2. RTI – Procedures Specific to Cohort 1

Monitoring of RTIs will take place during each 28-day post-vaccination period, and additionally during the RSV season after the first dose (even if it falls outside of the 28-day post-vaccination period). Monitoring for MA-RTIs and severe LRTIs will take place during the whole study period.

During each 28-day post-vaccination period, all RTIs will be reported, nasal turbinate samples will be collected as soon as possible after the onset of respiratory symptoms, and signs and symptoms will be recorded by the attending health care professional using the RTI Symptoms Form.

If, during the RSV season, but outside the 28-day post-vaccination period, a subject shows persistent (>48 hours) clinical symptoms of rhinitis (sneezing or runny nose or congestion) and persistence (>24 hours) of one or more of the following: cough, abnormal breathing, fever, lethargy or decreased appetite, the study site should be notified. Nasal turbinate samples will be collected as soon as possible after the onset of these combined respiratory symptomsa. When nasal turbinate samples are collected, the attending health care professional will record signs and symptoms of the RTI using the RTI Symptoms Form.

Nasal turbinate samples will not be collected if less than 7 days after the previous sample collection.

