### **9.2.2. Other Evaluations – RSV Infection**

RSV seropositivity of Cohort 1 subjects will be assessed by RSV EIA or virus neutralization assay at screening. The cut-off for seropositivity by EIA is a titer >10 EIA units and the cut-off by virus neutralization assay is a titer >4. *Note:* RSV-seropositive toddlers may be recruited if RSV seropositivity was assessed via either of these assays in a different study of the sponsor.

Nasal turbinate samples, taken from any Cohort 1 subject with an RTI during each 28-day post-vaccination period, and from any Cohort 1 subject with a combination of respiratory symptomsa during the RSV season (but outside of the 28-day post-vaccination period), and from any Cohort 1 subject with a MA-RTI or severe LRTI during the whole study period, will be assessed for the presence of RSV infection by RT-PCR. The actual dates and times of sample collection must be recorded in the eCRF or laboratory requisition form.

a Persistent (>48 hours) clinical symptoms of rhinitis (sneezing or runny nose or congestion) and persistence (>24 hours) of one or more of the following: cough, abnormal breathing, fever, lethargy or decreased appetite.

In addition, scheduled blood samples may be assessed for the presence of RSV antibodies by serology.

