### 11.3. Criteria for Exploratory Endpoints

#### 11.3.1. Definitions for Exploratory Endpoints

The exploratory endpoints shown below will be collected to assess the feasibility of, and gain expertise in the collection of such events for future studies.

- RSV MA-RTI: All subjects with RSV-RTI that is medically attended, ie when the subject's parent/legal guardian seeks medical attention outside of normal study procedures, including health care professional's visit to the home, clinic visit, emergency room attendance, and hospital admission. (*Note*: medical attention outside normal study procedures will as much as possible also be captured on the RSV Symptoms Form.)
- Severe LRTI: For subjects in Cohort 1, severe RSV-LRTI will be defined as the presence of severe LRTI as assessed by the CEC, and a positive assessment for RSV.

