##### 11.3.1.2. Determination of RSV Positivity

- A subject is considered RSV positive if he/she has a positive RT-PCR for RSV on nasal turbinate samples (central laboratory).

- If a RT-PCR test result for RSV is missing (ie, not available or not conclusive), the CEC will assess RSV positivity using all available clinical and laboratory information.

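### SAP Section 7 summarises RSV infection only if a severe LRTI occurs, and its confirmed category omits RT-PCR-positive children who lack the symptom combination

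*SAP*

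**What the plan says.** **Objective and promised analysis.** Protocol 2.1.1 lists, as an exploratory objective, assessing RSV infection rates in vaccine and placebo subjects. Protocol 11.6 commits to it: "Incidence of any RSV infection, as described in Section 3.2, in Ad26.RSV.preF and placebo subjects will be summarized by descriptive statistics".

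**SAP analysis.** SAP 7 opens with a condition: the summary is made if a severe LRTI is present in Cohort 1. Cases are then put in two categories and split by severity. The text does not mention arms. Suspected infection means rhinitis for more than 48 hours plus at least one other listed symptom for more than 24 hours. The second category is nested in the first: "Confirmed RSV infection: subject with suspected RSV infection and positive for RSV on the basis of RT-PCR conducted centrally". Protocol 3.2 uses the same pair.

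**Who is swabbed.** In RSV season, outside the post-dose windows, the symptom combination triggers a sample. Two other routes do not need it. After each dose: "During each 28-day post-vaccination period, all RTIs will be reported, nasal turbinate samples will be collected as soon as possible". At any time: "Throughout the study, nasal turbinate samples will be collected from any subject with a MA-RTI or severe LRTI". Protocol 9.2.2 sends all these samples for RT-PCR.

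**Other definitions of RSV infection.** The Protocol 2.1.2 endpoint reads "For Cohort 1 only, RSV infection confirmed by either reverse transcriptase polymerase chain reaction (RT-PCR), or by serology", the serology being for cases with no RT-PCR, with a fold-rise rule for asymptomatic infection. Protocol 11.3.1.2 makes a positive central RT-PCR sufficient and passes the judgement to the CEC when the result is missing or inconclusive. The per-protocol immunogenicity rule (Protocol 11.1, SAP 2.3.2.1) drops samples taken after a natural infection shown by RT-PCR or other sources. None of these mentions the combination.

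**The concern.** There are two problems, and the first is the larger.

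First, the SAP replaces an unconditional commitment with one that depends on a severe outcome. If no severe LRTI occurs, SAP 7 as written yields no infection summary, and the objective of assessing rates in the two arms has no specified answer. Making a table depend on the outcome also weakens it: a reader cannot tell an absent table from an absence of infections. SAP 1.6, which records changes to planned analyses, covers only the interim analyses, so the restriction does not appear there as a deliberate change.

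Second, when the summary does run, the confirmed count falls short of the endpoint in Protocol 2.1.2 by every RT-PCR-positive child who lacks the combination. Such a child could have later samples removed from the per-protocol immunogenicity analysis because of an RSV infection that the infection summary does not count.

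**Working it through.** **Plan's own figures.** The plan gives no RSV attack rate and no projected number of infections, so there is no figure on this point to reproduce. Its only numerical justification, the table of chances of seeing at least one AE, reproduces in all 28 cells (for example 1 − 0.99^24 = 21.4%, printed as 21%). It is not an input here.

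**Step 1: does the summary run?**
- Protocol 11.6: no precondition; vaccine and placebo subjects both named.
- SAP 7: runs only given a severe LRTI in Cohort 1; arms not named.
- Amendment 4 rationale: RSV-seropositive toddlers are at limited or no risk of severe RSV disease.

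The SAP trigger is a severe LRTI of any cause, so the Amendment 4 statement does not make the trigger impossible. It does mean that, in 36 healthy seropositive toddlers, the sponsor has no reason to expect it from RSV.

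**Step 2: where does an RT-PCR-positive child land if it does run?**

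| Reason for the sample | Combination needed for the sample? | SAP 7 and Protocol 3.2, if combination absent | Protocol 2.1.2 and 11.3.1.2 |
|---|---|---|---|
| Symptom combination in RSV season | Yes | Does not arise | RSV infection |
| Any RTI within 28 days of a dose | No | Neither category | RSV infection |
| MA-RTI, any time | No | Neither category | RSV infection |
| Severe LRTI, any time | No | Neither category | RSV infection |

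The last row matters because the CEC criteria in Protocol 11.3.1.1 (cough or difficulty breathing, fast breathing or low saturation, and a severe feature) do not include rhinitis. The event that triggers the summary could itself fall outside both categories. Infections shown by serology alone, and those judged positive by the CEC without an RT-PCR result, also cannot be confirmed under SAP 7.

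**Step 3: effect of one omitted subject.** Arm sizes are 24 and 12 (Protocol Table 5). SAP Table 1 still prints 32 and 16, but the SAP 1.2 text gives 36 toddlers, which matches 24 + 12.
- Active: 1/24 = 4.2 percentage points.
- Placebo: 1/12 = 8.3 percentage points.

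The documents do not give the share of RT-PCR positives without the combination. The total shortfall is therefore k × 4.2 or k × 8.3 points for an unknown k in each arm, and k may be zero.

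**Step 4: precision of a corrected table.** With assumed counts, only to show width, exact (Clopper-Pearson) 95% intervals are 4.7% to 37.4% for 4/24 and 5.5% to 57.2% for 3/12. They overlap almost entirely.

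**The case against.** The other side has several fair points.

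- **Protocol 11.6 can be read broadly.** It speaks of any RSV infection, and Protocol 3.2 also sets out the wider sampling. This is possible, but 11.6 ties the analysis to 3.2, and the only case criteria there are the two categories. The reading also does nothing about the SAP condition.
- **The separate data presentation specifications may hold the outputs.** SAP 1 says so, and a table of MA-RTI or a listing of RTI Symptoms Form data may be there. It would therefore be wrong to assert that those outputs are missing. The condition and the case definition, however, are set in SAP 7.
- **MA-RTI is collected for feasibility.** Protocol 11.3.1 says this of RSV MA-RTI and severe LRTI. This stands: the plan promises no comparison of MA-RTI rates, and the lack of one is not a fault in itself. The feasibility note does not cover the separate infection-rate objective.
- **Cases are not lost to safety review.** RTIs within 28 days of a dose are unsolicited AEs, serious RTIs are SAEs throughout, and any severe LRTI goes through the SAE system. This also stands. A reader might infer that RSV illness would go unseen; the documents do not support that. What is missing is a count of RSV infection by arm.
- **Few children may lack the combination.** Clinical course is followed to symptom resolution, so a child swabbed early may still meet the duration rule later. This is true, and it is one reason why the gap cannot be sized.

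Two further inferences go too far. The long stretch of follow-up outside the post-dose windows might be taken as the size of the gap. It is not, because many illnesses in that time will meet the combination or be RSV negative. A reader might also infer that the narrow definition would create a false advantage for the vaccine. That needs omissions concentrated in the active arm, for which the documents give no evidence.

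**Conclusion.** The point holds, at low weight. Followed as written, SAP 7 gives no RSV infection summary unless a severe LRTI occurs. If one does occur, it gives a confirmed count that can fall below the Protocol 2.1.2 endpoint. The first part follows directly from setting SAP 7 against Protocol 11.6. How likely the summary is to be skipped rests on the sponsor's own expectation of little or no severe RSV disease, and the documents give no probability. The second part follows from the definitions and the sampling rules. Its size is 4.2 points per omitted active subject and 8.3 per omitted placebo subject, multiplied by a number that the documents do not supply, and no direction of bias between arms can be claimed. The objective is exploratory, no hypothesis is tested, and the primary safety and the immunogenicity conclusions do not depend on it.

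**What to change.** In SAP 7, delete the opening condition. For Cohort 1, over the whole follow-up and by regimen, report the number and percentage of subjects with:

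1. **RSV infection per Protocol 2.1.2**, on separate lines: central RT-PCR positive, split into with and without the symptom combination, so that confirmed per Protocol 3.2 stays visible as a subset; judged positive by the CEC where RT-PCR is missing (Protocol 11.3.1.2); and serology-based, where assayed. Serology needs its own line because 2.1.2 allows a rise in F antibody to count only in placebo subjects.
2. **RSV MA-RTI per Protocol 11.3.1**, as a plain count in keeping with its feasibility purpose.

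The severe/non-severe split can stay. A listing of RTI Symptoms Form data is optional and may already be in the data presentation specifications.

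The cost is some SAP wording and one small descriptive table from data already planned for collection; no new visits, samples or subjects. The drawback is that the counts will be small and imprecise, so the table should carry a note that it cannot separate the arms.
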